4 STUDY SETTING

This multi-centre study is hosted by East London NHS Foundation Trust as the coordinating centre and will take place across the following NHS Trusts and Universities: East London NHS Foundation Trust; Tees, Esk & Wear Valleys NHS Foundation Trust in collaboration with the University of York; Devon Partnership NHS Trust in collaboration with the University of Exeter and Oxford Health NHS Foundation Trust. Participants across all sites will be identified through primary care or secondary care mental health services.

Patient and clinician participants will be recruited, the intervention will be delivered and research data collected in quiet rooms within facilities of all these Trusts or participating Universities, which contain the following sites: East London, Luton, Bedfordshire, North East (York, North Yorkshire, Teeside and Durham), Devon, Oxfordshire, Buckinghamshire, Swindon, Wiltshire, Bath and North East Somerset. If patient participants prefer so, there will be the option to carry out research assessments at their homes or other community locations. Researchers will follow the lone worker policy of their respective participating NHS trusts.

5 ELIGIBILITY CRITERIA

5.1 Inclusion criteria

Patients:

- 18-65 years old
- Diagnosis of psychosis-related condition (ICD-10 F20-29)
- Capacity to provide informed consent
- Ability to communicate in English
- Limited social network size and low quality of life (Score 5 or less on MANSA quality of life assessment and less than 7 consecutive days with social contacts in the previous week)

Clinicians:

- Mental health professional with experience of providing community mental health care (e.g. psychiatrists, clinical psychologists, nurses, occupational therapists)
- Aged 18-65 years old
- Employed by participating NHS Trusts
- Capacity to provide informed consent
- Ability to communicate in English

5.2 Exclusion criteria

Patients:

- Does not meet inclusion criteria
- Primary problem of current drug addiction
- No capacity to provide written informed consent
- An inpatient on a psychiatric ward at the time of recruitment

Clinicians:

- Does not meet inclusion criteria

6 STUDY PROCEDURES

Please see Appendix 1 for schedule of procedures.

This study is part of a larger programme of research to improve social networks and quality of life in people with psychosis. It will test the feasibility of the intervention for use in the NHS; check the feasibility of recruitment and randomisation procedures and test different methods for assessing adherence to the manual, which will be used in the subsequent randomised controlled trial. It will also help to gain further and more systematic practical experience with the intervention in the NHS and refine methods for assessing the costs of the intervention in preparation to a future larger trial.

This specific study will also explore experiences of patients and clinicians who will receive or deliver the intervention in practice and help further refinement and specification of the intervention before the next phase of this programme, a full randomised controlled trial.

Consent

Potentially eligible patients will be identified by members of the clinical team, who will introduce the study and, if interest is shown, request their verbal permission to pass their contact details to a member of the research team. We would also use a data base of the patients that took part in the previous work package, the SCENE survey, and have expressed an interest to participate in the intervention.

The clinician delivering the intervention will not be the treating clinician of a participating patient and this will be clarified when explaining the study and the intervention before taking consent. Informed consent will be sought from all patients to participate in this study, which will include permission to access medical records to retrieve socio-demographic and clinical characteristics. During the baseline interview researchers will ascertain whether patients meet the inclusion criterion of “score 5 or less on the MANSA less than 7 consecutive days with social contacts in the previous week”. If the service user is not eligible to join this study they will be still compensated £15 for their time. They will also be reassured that they will resume care as usual, e.g. with their Community Mental Health Team.

If participants are eligible, they will be invited to take part in the study. Participants will be given the option during the consent process to receive a copy of the findings from the study. This will be a lay summary of results developed with the assistance of the LEAP. Informed consent will be sought from clinicians as well.

The assessment of capacity will be done in two stages: in a first stage (when obtaining permission to be contacted by research team) this will be conducted by mental health clinicians who are trained and experienced in this assessment which is part of their everyday clinical practice. In a second stage

(when obtaining consent), researchers will assess capacity to consent to the participation in the study. The researchers will have experience in mental health studies and will be trained by experienced clinicians ([name] and [name]) in assessing capacity to consent to research. At each session of the intervention the capacity to consent to treatment will be ascertained by the delivering clinician according to common clinical practice.

Baseline assessment with the researcher

Demographic and clinical characteristics data collection

Research team member will complete a case report form (CRF) recording patients' responses about demographic and clinical characteristics, such as the diagnoses, duration of illness, number of voluntary and involuntary hospitalisations, current medication, history of psychological and other treatments and record this on a form. Alternatively, participants will be given the option to complete this for themselves. Any information that patients are unable to provide will be collected from patients' medical records with their consent. We would use a shortened version of the Client Service Receipt Inventory (CSRI – 'Generic' UK Mental Health, Beecham and Knapp, 2011) for this. Then the research team member will conduct clinical assessment of the current positive and negative symptoms using two validated measures: Positive And Negative Symptom Scale, (PANSS, Kay, 1991) and Clinical Assessment Interview for Negative symptoms (CAINS, Kring et al., 2013) for a more specific measurement of different aspects of negative symptoms.

Social contacts and activities

The number and quality of social contacts on each day of the previous week will be measured ([name] et al., 2016), including detailed questions about social activities as developed in the on-going PGfAR VOLUME (on volunteering in mental health) and including questions of the Time Use Survey ([name] et al., 2016). In addition to the questions from the Time Use Survey we ask about the price of each activity in order to estimate what activities would be reasonable to offer during the intervention.

Quality of life and loneliness assessments

The researchers will collect the information on subjective quality of life (MANSA, [name] et al., 1999) health-related quality of life (EQ-5D-3L, Rabin et al., 2014), and ICEpop CAPability measure for Adults, which is a measure of capability for the general adult (18+) population for use in economic evaluation (ICECAP-A, Al-Janabi et al., 2013). Unlike most profile measures used in economic evaluations, the ICECAP-A focuses on wellbeing defined in a broader sense, rather than health. We also assess subjective loneliness through UCLA-8 loneliness scale (Hays and DiMatteo, 1987) and Global Rating of Loneliness.

During the baseline interview, researchers will ascertain whether patients meet the inclusion criterion of having "quality of life score 5 or less" using the MANSA ([name] et al., 1999). If yes, they will be invited to participate in the intervention.

Randomisation procedures

Patients will be randomised to either the intervention or control. The allocation ratio will be 2:1 in favour of the intervention. Randomisation will be stratified by NHS Trust, ensuring balance between

groups in the patient numbers from each NHS Trust. Blocked randomisation with a block size of $m=3$ will be used within each stratum. A fixed block size of $m=3$ is appropriate in this trial as the feasibility of intervention and study procedures is of primary interest and not intervention effects. Should blocked randomisation be used in the full trial a variable block size would be utilised.

The randomization will be carried out remotely by the Pragmatic Clinical Trials Unit at Queen Mary, University of London. The PCTU will inform the research team of the results of the allocation by secure email using a password protected file.

Intervention

a. Type and frequency of meetings

Patients will be identified from mental health teams' caseloads and will be offered the intervention if they do not show substantial risk to self or others and this should be monitored as per routine clinical practice. The clinician delivering the intervention will not be the treating clinician of the patient.

Clinicians should meet patients six times over the six-month intervention period; about once per month.

The intervention should start with a sufficiently long first two meetings (about 60 minutes) in the first month to explore preferences, discuss options in detail and agree on the way forward. The following meetings should discuss progress and provide support as required. They should last at least 20 minutes. Further contacts of clinicians with patients, as needed via telephone, text messages, Skype or other electronic means, will be encouraged. Such contacts may also replace face-to-face contacts, but the initial meeting and at least one more meeting will be face-to-face. The location of these meetings can vary and depend on patient preference and local circumstances (including patients' homes, community places and offices of services).

b. Content of meetings

The meetings should focus on the patient's motivation to expand social networks, their preferences for how to do this, local options for doing this and plans for how to achieve it in practice. This may include temporary support through the intervention (e.g. reminders, initial accompanying). The planned activities should be a way to expand social networks, e.g. leisure activities in groups rather than going to the cinema on their own. This will usually mean establishing new contacts, but could also be engaging in new joint activities with previous contacts (outside on-going friends and close family). The intervention will not address potential difficulties in already existing on-going relationships (e.g. with close family).

The meetings should start with a review of progress and should end with an agreement on actions to be taken. This will then be reviewed and possibly revised at further meetings. Normally, the agreement should not specify more than one type of concrete activity at a time. If a patient expresses interest in more than one activity, they should be asked to choose one to prioritise. If there is no substantial progress after three months with one type of activity, an agreement should be made to switch to a different activity. There will be some flexibility about when exactly the switch should be considered and agreed. The switch should be agreed by both patient and clinicians in a face-to-face meeting.

c. Who will deliver the intervention

The intervention will be delivered by employed NHS clinicians who are clinically qualified (e.g. psychiatrists, psychologists, nurses, occupational therapists) and have experience in delivering psycho-social interventions.

d. Training of clinicians

Clinicians will be trained in the intervention in one session of up to three hours, flexibly in either a group format or individual format by a senior member of the core research team. When and if required, depending on the previous experience, additional one-to-one training can be provided.

During the training they will acquire knowledge of the structure and aims of the intervention, i.e. number of sessions, frequency of sessions and procedures to help the patients to reach out to social activities. They will also be taught simple motivational interviewing techniques. Scenarios in which barriers for the patient in engaging in new social contacts may appear and strategies to overcome them will be discussed.

Knowledge about the local context will be helped by a list of possible local options for low cost activities in the local area available to the patient that involve contacts with other people. This list will be provided by the research team. Clinicians will also be expected to and supported in obtaining a good knowledge about the options and encouraged to network in the given community to generate more options for relevant activities. Learning progress will be assessed during the training and in the subsequent supervision, provided by senior members of the research team, which will be organised flexibly in order to identify the ideal frequency. At the end of the case studies, clinicians who have delivered the intervention will receive an in-depth interview and will be encouraged to provide suggestions for further refinement of the intervention, of the training and of the supervision arrangements.

e. Further support of clinicians

Clinicians will receive updates on changes in options for activities from the local research team and from participating clinicians themselves through networking. They will also be supervised through regular phone calls (at least once a month or more if and as required) either locally or centrally from the study team in London.

Recording of the intervention sessions

For each clinician, we will aim to audio-record three interventions sessions (if the patients consent to this). They will be helpful to understand what are the topics and activities discussed during the intervention sessions and to identify ways to help motivation and commitment of patients to social activities in order to help specify training guidelines and obtain examples to be used for a training package.

Control group

Patients in the control group will be provided with comprehensive information about local options for social activities by the researcher. This group is intended to control for the provision of information and non-specific attention through a professional in addition to routine care. Also, the mere provision of information should be regarded as good practice independent of additional targeted interventions, so that patients in the control group should receive it too.

The usual treatment, including care-coordination, medication, and psychological therapies, will not be affected, neither in the intervention nor in the control group.

Follow-up quantitative interviews with a researcher

This applies to both the intervention and control groups. All participants from the intervention group, and half of the control participants, chosen at random, will complete the follow-up. Participants will fill out the same questionnaires as during baseline assessment:

- Sociodemographic information;
- Client Service Receipt Inventory, (CSRI, Beecham and Knapp, 2011);
- Positive And Negative Syndrome Scale (PANSS, Kay, 1991);
- Clinical Assessment Interview For Negative Symptoms (CAINS, Kring et al., 2013);
- Social Contacts Assessment (SCA, [name] et al., 2016);
- Time Use Survey (TUS, [name] et al., 2016);
- Manchester Short Assessment of Quality of Life questionnaire (MANSA, [name] et al., 1999);
- EQ-5D-3L (Rabin et al., 2014);
- ICECAP-A (Al-Janabi et al., 2013);
- Global rating of Loneliness;
- UCLA Loneliness Scale (Hays and DiMatteo, 1987);

Client Satisfaction Questionnaire (Attkinsson and Zwick, 1982) will be added at the follow up assessment in order to evaluate satisfaction with the intervention.

In-depth (qualitative) interviews

Clinician and patient interviews will be conducted to assess their experiences of the intervention. All interviews will be audio-recorded and facilitated by a researcher using a topic guide. Patient interviews will take place at the end of their intervention, and clinician interviews will be conducted when they have completed interventions for all of their patients. Interviews will last between 45-60 minutes and will take place in quiet rooms across NHS sites, quiet rooms at the participating Universities or in patients' homes. We plan to conduct the interviews with 32 patients who took part in the intervention and with 8 out of 16 control participants. We will have sufficient time (9 month allocated to the study) and resources (we can rely on the help from CSOs) to conduct, record and analyse those interviews.

Payment to participants:

Patients taking part in baseline and post-intervention interviews will be offered £15 cash or voucher as a reimbursement for their time for each interview (maximum £30). Clinician participants will not be reimbursed for their time as the intervention sessions will take place during their working hours. The commitment required is not likely to have a significant effect on their working time and the participation of the clinicians will be discussed with their line managers and team leads.

Adherence to manual

Adherence to manual will be assessed through the use adherence checklist, routine documentation (recording document after each session), and audiotapes of patient professional meetings (as far as these can be collected).

Economic evaluation

We will assess costs related to delivery of the intervention based on the professionals involved and the number of sessions offered. We will also collect use of services in the experimental and control group by retrospective participant self-report using a relevantly modified version of the Client Services Receipt Inventory. We will use the EQ-5D-3L and ICECAP-A and evaluate their ease of administration and patterns of missing data in order to choose the final measure to use for cost-effectiveness analysis in the subsequent large trial.

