Sponsor	
East London NHS Foundation Trust Noclor Research Support [name] St Pancras Hospital [name] [contact] Email: [contact]

Funder(s)	
National Institute for Health Research Programme Grant for Applied Research Central Commissioning Facility [name]

Clinical Trials Unit	Pragmatic Clinical Trials Unit (PCTU) Centre for Primary Care and Public Health Blizard Institute [name] [contact]
Key Protocol Contributors	[name] [name] [name] Unit for Social and Community Psychiatry Newham Centre for Mental Health [name] [contact] Emails: [contact] ; [contact] ; [contact]
Statistician	[name] Pragmatic Clinical Trials Unit (PCTU) Centre for Primary Care and Public Health Blizard Institute [name] [contact] Email: [contact]
Committees	Programme Management Group (co-applicants), Lived Experience Advisory Group, Steering Committee

STUDY SUMMARY

Study Title	Feasibility Trial Of A Structured Intervention For Expanding Social Networks In Psychosis
Internal ref. no. (or short title)	SCENE (WP4)
Study Design	Feasibility trial
Study Participants	
Patients with a diagnosis of a psychosis-related condition (ICD10 F20-29); aged 18-65; capacity to provide informed consent; ability to communicate in English; 5 or less score on the quality of life assessment (MANSA) and less than 7 consecutive days with social contacts in the previous week.
 
Mental health professionals: aged 18-65; with experience of providing mental health care; employed by participating NHS Trusts; capacity to provide informed consent; ability to communicate in English

Planned Sample Size	12 clinicians and at least 48 patients at four sites (East London, York, Exeter and Oxford); 32 patients will be randomised to receive the intervention. All patients will be interviewed at baseline to check eligibility. The intervention will be delivered by experienced clinicians who will be trained in it by the research team.
Study duration	9 months
Planned Study Period	01 st of June 2018- 28 th of February 2019

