6.5 Future Study

If following this feasibility trial there will be no major amendments to the intervention or research procedures, we will propose to the independent Programme Steering Group that: a) we will continue recruitment for a full hypothesis testing randomised controlled trial; b) we will use participant data from the feasibility trial (WP4) in the subsequent full randomised controlled trial (Work Package 5).

If the independent Programme Steering Group will approve our proposals we will submit the protocol for the full randomised controlled trial to the ethics committee as a major amendment.

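### A fixed block of 3 at 2:1 within Trust could let a recruiter know up to 44% of allocations in advance, and the reason given for it is in tension with the conditional reuse of the data in Section 6.5

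*Protocol*

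**What the plan says.** Protocol Section 6, Randomisation procedures, sets the scheme: "The allocation ratio will be 2:1 in favour of the intervention"; "Randomisation will be stratified by NHS Trust"; "Blocked randomisation with a block size of $m=3$ will be used within each stratum". The reason follows: "A fixed block size of $m=3$ is appropriate in this trial as the feasibility of intervention and study procedures is of primary interest", with intervention effects named as not being the primary interest. The same paragraph says that the full trial, if blocked, would use a variable block size.

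The Pragmatic Clinical Trials Unit (PCTU) randomises remotely, and then: "The PCTU will inform the research team of the results of the allocation by secure email using a password protected file". The research team also takes consent (Section 6, Consent; Section 6.2) and confirms the MANSA eligibility criterion at the baseline interview (Section 6.1.1). Under Section 6, Control group: "Patients in the control group will be provided with comprehensive information about local options for social activities by the researcher".

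The Study Summary plans "at least 48 patients at four sites (East London, York, Exeter and Oxford"), and Section 7.2 gives 48 patients with 32 randomised to the intervention.

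Section 6.5 says that, if no major amendments to the intervention or research procedures are needed, the team will propose to the independent steering group that recruitment continues into a full hypothesis-testing trial and that "we will use participant data from the feasibility trial (WP4) in the subsequent full randomised controlled trial (Work Package 5"). If the group approves, the full-trial protocol goes to the ethics committee as a major amendment.

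**The concern.** Three is the smallest block that can deliver 2:1, and each block holds only one control. Once that control has been drawn, the rest of the block is known, and the third place is always known. Remote generation hides the list, but it does not stop someone who knows the block size and the earlier results from deducing the next one.

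The people who could make this deduction also have some control over who enters and when. Sections 6.1.1 and 6.2 allow the baseline interview on the same day or after up to a week. Section 2.1 expects some patients to be upset by allocation to control, which is a well-meant motive for timing an entry. If entry were timed by expected arm, the arms could differ at baseline in ways that randomisation is meant to prevent.

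For a stand-alone feasibility study this might be tolerable, and that is the protocol's argument. But Section 6.5 declares a plan under which the same participants would count in a hypothesis-testing comparison. Their allocations would by then have been made under the fixed scheme.

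**Working it through.** **Inputs.** Ratio 2:1, block of 3, strata by NHS Trust (Section 6, Randomisation procedures); four sites (Study Summary); 48 patients, 32 to intervention (Section 7.2). The protocol gives no predictability figure.

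**The plan's own figure.** 48 × 2/3 = 32 intervention and 16 control. This reproduces. 48/3 = 16 complete blocks; if recruitment is even, 48/4 = 12 patients, or 4 blocks, per Trust. The protocol sets no quota per Trust, so 12 is an assumption.

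**Certain allocations, block of 3.** The three orders are equally likely (I = intervention, C = control). An allocation is certain when all places left in the block belong to one arm.

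| Order | 1st known? | 2nd known? | 3rd known? | Number known |
|---|---|---|---|---|
| C I I | no | yes | yes | 2 |
| I C I | no | no | yes | 1 |
| I I C | no | no | yes | 1 |

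Mean per block = (2 + 1 + 1)/3 = 4/3. Share = (4/3)/3 = 4/9 = 44.4%. Over 48 patients: 48 × 4/9 = 21.3.

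**Best-guess accuracy.** The first place is guessed I and is right 2/3 of the time. At the second place, after C (probability 1/3) the next is I for certain; after I (probability 2/3) it is a coin toss: 1/3 + 2/3 × 1/2 = 2/3. The third place is always right. Mean = (2/3 + 2/3 + 1)/3 = 7/9 = 77.8%. Always guessing intervention, with no knowledge, is right 2/3 = 66.7% of the time.

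**Alternatives.** These were obtained by enumerating all sequences, with 12 patients per Trust for the mixed schemes. The observer is assumed to know which sizes are in use but not their order; under closure, the observer also knows the total of 12.

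| Scheme | Certain in advance | Best guess right |
|---|---|---|
| Fixed 3 (protocol) | 44.4% | 77.8% |
| Fixed 6 | 13/45 = 28.9% | 74.4% |
| Random 3 and 6, forced to close at 12 | 17.1% to 18.9% | 76.1% |
| Random 3 and 6, no forced closure | 8.9% | 75.0% |

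The range under closure depends on the sequences allowed: all five orders of 3s and 6s that sum to 12, or only the three orders of 3, 3, 6.

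**Price of not forcing closure.** With sizes 3 and 6 equally likely, the chance that a block ends at place 3 is 1/2; at place 6, 1/2 × 1/2 + 1/2 = 3/4; at place 9, 1/2 × 3/4 + 1/2 × 1/2 = 5/8. A block of 6 then starts at place 10, and is cut in half at 12, with probability 5/8 × 1/2 = 5/16. Half of a 4:2 block contains 3 or 1 interventions instead of 2 with probability (4 + 4)/20 = 2/5. So a Trust that stops at 12 has 9:3 or 7:5 instead of 8:4 with probability 5/16 × 2/5 = 1/8, and is never further from it.

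**The case against.** The strongest defence is that the authors considered the matter. They say openly that effects are not of primary interest in this trial, Section 7 rules out efficacy tests, and variable blocks are reserved for the full trial. Reuse under Section 6.5 needs no major amendments, a proposal to the independent steering group and its approval. A reader might infer that Section 6.5 flatly contradicts the defence of the fixed block. It does not: the reuse is conditional, and the defence speaks of this trial only. What remains is a tension, because the stated conditions do not ask how predictable the allocations were, and a later change of scheme does not reach back.

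A reader might also take 44% as what recruiters will in fact know. The document does not support that. It says that the research team is told, not that each recruiter sees every result in the Trust or that each result arrives before the next consent. Section 4 lists several areas under some Trusts, so a stratum may have more than one recruiter. Incomplete blocks would also lower the share slightly. The figure is a ceiling.

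Nor does the document show that the recruitment and refusal rates would be distorted. Clinical teams identify and first approach patients, they are not named as recipients of the allocation e-mail, and refusal is the patient's decision. MANSA records the patient's own view of quality of life, which leaves less room for steering by scoring than by timing.

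Finally, a reader might infer a fault of assessor blinding, since researchers learn the arm and symptom scales are repeated at follow-up. The protocol claims no such blinding, so nothing is contradicted. The matter does not depend on block size, and a remedy would mean splitting roles at small sites. It is not part of this point.

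**Conclusion.** The point holds as a weakness of allocation concealment that can be removed at almost no cost. Up to 4/9 of allocations (44%, about 21 of 48) could be known in advance, and best-guess accuracy could reach 78% against 67%. This rests on complete blocks, randomisation one patient at a time, and a recruiter who knows the block size and has seen every earlier allocation in the Trust. The protocol makes these conditions plausible but does not state them all. The finding is a risk of selection bias, not shown bias.

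The stated reason covers WP4 only as a stand-alone feasibility study. It sits badly with a declared, though conditional, plan to carry these data into a hypothesis-testing trial. Because no efficacy test is planned in WP4 itself, this is a change that should be made, not a flaw that invalidates the study.

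**What to change.** From the start of WP4, have the PCTU use randomly varied block sizes in multiples of three (for example 3 and 6) within each Trust. Keep the sizes out of the protocol and undisclosed to recruiting researchers. In Section 6, Randomisation procedures, replace the statement of the block size with one that blocks vary at random and that the sizes are held by the PCTU, and delete the sentence defending the fixed block of three.

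Do not force the sequence to close at 12 per Trust. Closure roughly doubles the certain share (17% to 19% against about 9%), and the protocol does not promise exactly 12 patients per Trust. The main gain is in certainty: best-guess accuracy falls only from 78% to about 75%, because 2:1 allocation alone makes intervention the better guess.

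The cost is a change to the list specification and to a few lines of text, since the PCTU already generates the allocation remotely. The downside is that a Trust whose last block is incomplete may depart slightly from exactly 2:1: with 3s and 6s and 12 patients, by one patient with probability 1/8.
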